	
abnormalities, such as elevated CRP and d-dimer levels, hypoalbuminemia, renal dysfunction, and effusions, are also observed in Covid-19, as they are in cytokine storm disorders. Laboratory test results reflecting hyperinflammation and tissue damage were found to predict worsening outcomes in Covid-19.
 
CimetrA, comprising Curcuma longa rhizome dry extract and Boswellia serrata resin dry extract in a nanoparticulate formulation, was studied on patients with the novel corona virus SARS-CoV-2 in randomized double blind control Phase II study (MGC-006 – under a previous product name - ArtemiC). The study product demonstrated excellent safety and efficacy profiles.
 
In the in vitro clinical trial CimetrA demonstrated the ability to reduce cytokines elevation in PBMC induced cell tissue.

Study Purpose	This study designed to evaluate the efficacy, pharmacokinetic parameters, and safety of CimetrA on patients diagnosed with COVID-19.
Methodology and study procedures	
Multi-center multinational-controlled study in Israel, Brazil, South-Africa and the United States.
 
240 adult patients who suffer from moderate COVID-19 infection.
 
Safety will be assessed through collection and analysis of adverse events, blood and urine laboratory assessments and vital signs.
 
After Screening visit, the study drug will be administered twice a day morning and evening (every 12 hours) during (day 1 and day 2)
 
The patients will be randomized in 1:1:1 ratio to study drug (CimetrA) in two dosages in addition to Standard of Care - Arm 1, 2 or (Placebo) in addition to Standard of Care- Arm 3.

Study Duration	Study will take place during patient's hospitalization due to COVID-19 infection. The study will last up to 4 weeks, until conclusion on day 28. In case of hospital discharge within the study period, follow up will continue per protocol until day 28 wherever the subject will be located, performed via phone call or in-clinic, depending on the status of the patient and study schedule.
Study Endpoints	The primary outcomes:

	MGC Pharma Clinical Study Protocol	Protocol No.: MGC-009
		Version 02, 05 Sep 2021
		Page 5 of 76
A Phase IIb, double blind, placebo-controlled clinical study designed to evaluate the effect of CimetrA in patients diagnosed with COVID-19		CONFIDENTIAL

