9. STUDY ENDPOINTS

9.1. The primary outcomes:

- **Efficacy endpoint**

- 1- Change in WHO Ordinal Scale for clinical improvement (baseline to end of study will be measured on days 1,7,14 and 28).

The World Health Organization (WHO-WHO) has proposed the “Ordinal Scale of Clinical Evaluation of the World Health Organization” presented below as a means of generating a numerical value to assess the health status of the participant to allow comparisons to be made in clinical studies. The scale is shown in the table below and will be used to assess a secondary effectiveness target in this study.

Patient State	Descriptor	Score
Uninfected	Uninfected; no clinical evidence and viral RNA detected	0
Ambulatory	Symptomatic; independent	1
	Symptomatic; assistance needed	2
Hospitalized: Moderate diseases	Hospitalized, no oxygen therapy	3
	Hospitalized; oxygen by mask or nasal prongs	4

	MGC Pharma Clinical Study Protocol	Protocol No.: MGC-009
		Version 02, 05 Sep 2021
		Page 34 of 76
A Phase IIb, double blind, placebo-controlled clinical study designed to evaluate the effect of CimetrA in patients diagnosed with COVID-19		CONFIDENTIAL

Hospitalized: Severe diseases	Hospitalized; oxygen by NIV or high flow	5
	Hospitalized; mechanical ventilation	6
	Mechanical ventilation and vasopressors, dialysis or ECMO	7
Dead	Dead	8

2- Change in COVID-19-Related Symptoms score (measured on days 1,7, 14, 28)

• **Safety Endpoints**

Safety will be assessed through collection and analysis of adverse events, blood and urine laboratory assessments and vital signs.

9.2. **The secondary outcomes:**

- Number of participants with depending on oxygen supplementation through day 28 since onset of symptoms
- Change in inflammatory marker levels - IL-6, IL-1 β , IL-12, TNF α , IFN- γ , CRP, NLR (Neutrophil / Lymphocyte ratio) (days 1, 2, 4, 7) compared to baseline
- Pharmacokinetic profile of the study drug on day 1 through 24 Hrs.
- Incidence and duration of mechanical ventilation
- Incidence of Intensive Care Unit (ICU) stay during COVID-19 complication
- Percentage of participants with definite or probable drug related adverse events
- Long term adverse events of COVID-19 on Day 28
- The Impact covid_19 on quality of life of patients on Days 1, 14 and 28

9.3. **The exploratory outcomes:**

- Course of change in D Dimer levels compared to baseline

	MGC Pharma Clinical Study Protocol	Protocol No.: MGC-009
		Version 02, 05 Sep 2021
		Page 35 of 76

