10. STUDY DESIGN AND PROCEDURES

240 adult patients who suffer from COVID-19 infection and do not participate in any other clinical trial. Patient must not agree to participate in any new clinical study during the study duration. Study will take place during patient's hospitalization due to COVID-19 infection. The study will last up to 4 weeks, until conclusion on day 28. In case of hospital discharge within the study period, follow up will continue per protocol until day 28 wherever the subject will be located, depending on the status of the patient and study schedule.

If patient discharged, visits will be performed via phone call, if he still hospitalized, visits will be performed at corona department.

Only on day 28, all the patients must undergo clinic visit, they will arrive to the research clinic (only patient who will be under quarantine will have a phone call visit).

The study is not designed to include participants from a special population, so that patients with mental and intellectual problems, lack of judgment, children under the age of 18 and pregnant women will not be allowed to participate, or any patient who have a legal guardian.

Standard of care treatment acceptable to be used while patient participates in study:

Treatment will include:

Supportive care - symptomatic

Painkillers

Anticoagulant therapy

	MGC Pharma Clinical Study Protocol	Protocol No.: MGC-009
		Version 02, 05 Sep 2021
		Page 36 of 76
A Phase IIb, double blind, placebo-controlled clinical study designed to evaluate the effect of CimetrA in patients diagnosed with COVID-19		CONFIDENTIAL

Steroids

REMDESIVIR - Compassionate treatment

Antibiotic treatment as needed

Inhalations if necessary

Oxygen

The treatments offered above are given according to the guidelines of the Ministry of Health.

The treatment will be given to the patient according to the clinical judgment of the medical staff and in accordance with the patient's health condition, and therefore the treatment does not have to be the same in each of the medical centers participating in the study.

10.1. **Enrollment**

Each candidate subject will be reviewed for an inclusion/exclusion criteria. After signing the ICF, the candidate subject will be asked to provide a medical history and undergo a physical examination, including measurement of blood pressure, pulse, temperature (PO), body weight and height, saturation, respiratory rate, vas scale, news score.

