Biochemistry blood test: Sodium (Na), Potassium (K), Chloride (Cl), Creatinine, Glucose, Urea, Albumin, Calcium total, Alkaline Phosphatase (ALP), ALT, AST, Total Bilirubin, Direct Bilirubin, LDH, Total Protein, Uric Acid, CRP, and Lipid Profile (including Total Cholesterol, HDL, LDL, Triglycerides).

Hematology blood test: complete CBC.

D-Dimer test (coagulation): one tube for coagulation test

Inflammatory markers: the blood will be centrifuged and frozen according to the Lab manual, Local Lab.

Vital signs: blood pressure, pulse, weight, weight, body temperature (PO), saturation, respiratory rate.

VAS scale: will be performed by study staff member.

WHO Ordinal Score: will be completed by the study staff member based on patient status.

COVID-19-Related Symptoms assessment: will be completed by the study staff member based on patient status and answers.

COVID-19–Impact on Quality-of-Life Questionnaire: will be completed by the study staff member based on patient answers.

	MGC Pharma Clinical Study Protocol	Protocol No.: MGC-009
		Version 02, 05 Sep 2021
		Page 40 of 76
A Phase IIb, double blind, placebo-controlled clinical study designed to evaluate the effect of CimetrA in patients diagnosed with COVID-19		CONFIDENTIAL

POST- COVID-19 Functional Status Scale: will be completed by the study staff member based on patient answers.

Pregnancy test: women of childbearing potential must undergo a urine pregnancy test.

Physical examination: full examination by doctor.

** Measurements will be performed per institutional schedule by the hospital staff, not necessarily by the principal investigator or the sub-investigators.

PK parameters*: will be performed only on 14 patients that will agree to participate in the PK analysis (only for Brazil and South Africa).

The PK will be performed only for the first dose of drug, after patient received the first dose (5 puffs) the study staff need to follow the table below.

For each test, approximately 5 ml of blood will be drawn (equivalent to one teaspoon) total of 55 ml of blood will be drawn.

Table 6: List of time points for pharmacokinetic assessments

Study Visit Number 1	
Time point 0	Dosing (before the first dose of the drug)
Time Point 1	15 minutes post dose
Time Point 2	30 minutes post dose
Time point 3	45 minutes post dose
Time point 4	1 h post dose
Time point 5	1.5 h post dose
Time point 6	2 h post dose
Time point 7	4 h post dose
Time point 8	6 h post dose
Time point 9	8 h post dose

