- Hematology blood test **

	MGC Pharma Clinical Study Protocol	Protocol No.: MGC-009
		Version 02, 05 Sep 2021
		Page 43 of 76
A Phase IIb, double blind, placebo-controlled clinical study designed to evaluate the effect of Cimetra in patients diagnosed with COVID-19		CONFIDENTIAL

- Biochemistry blood test **
- Blood test for inflammatory markers (IL-6, IL-1 β , IL-12, TNF α , IFN- γ) (local)
- VAS scale

Day 7

- Concomitant Medications
- AE assessment
- Physical Examination
- Vital Signs
- Hematology blood test (local, mandatory even if there are available results from the day before)
- Biochemistry blood test (local, mandatory even if there are available results from the day before)
- WHO Ordinal Score
- COVID-19-Related Symptoms assessment
- Blood test for inflammatory markers (IL-6, IL-1 β , IL-12, TNF α , IFN- γ) (local)
- D-Dimer test (local)
- VAS scale
- COVID-19–Impact on Quality of Life Questionnaire

Days 8-13

- Concomitant Medications
- AE assessment
- Physical Examination
- Vital Signs

	MGC Pharma Clinical Study Protocol	Protocol No.: MGC-009
		Version 02, 05 Sep 2021
		Page 44 of 76
A Phase IIb, double blind, placebo-controlled clinical study designed to evaluate the effect of CimetrA in patients diagnosed with COVID-19		CONFIDENTIAL

- Hematology blood test **
- Biochemistry blood test **
- VAS scale

Day 14

- Concomitant Medications
- AE assessment
- Physical Examination
- Vital Signs
- Hematology blood test (local, mandatory even if there are available results from the day before)
- Biochemistry blood test (local, mandatory even if there are available results from the day before)
- WHO Ordinal Score
- COVID-19-Related Symptoms assessment
- Blood test for inflammatory markers (IL-6, IL-1 β , IL-12, TNF α , IFN- γ) (local)
- D-Dimer test (local)
- VAS scale
- PCR test for detection COVID-19
- COVID-19–Impact on Quality of Life Questionnaire

Day 21 (phone visit)

- Concomitant Medications
- AE assessment
- VAS scale
- COVID-19–Impact on Quality of Life Questionnaire WHO Ordinal Score

	MGC Pharma Clinical Study Protocol	Protocol No.: MGC-009
		Version 02, 05 Sep 2021
		Page 45 of 76
A Phase IIb, double blind, placebo-controlled clinical study designed to evaluate the effect of CimetrA in patients diagnosed with COVID-19		CONFIDENTIAL

- COVID-19-Related Symptoms assessment

Day 28 – Follow Up (clinic visit)

- Concomitant Medications
- AE assessment
- Physical Examination
- Vital Signs

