- Hematology blood test (local, mandatory even if there are available results from the day before)
- Biochemistry blood test (local, mandatory even if there are available results from the day before)
- WHO Ordinal Score
- COVID-19-Related Symptoms assessment
- Blood test for inflammatory markers (IL-6, IL-1 β , IL-12, TNF α , IFN- γ) (local)
- D-Dimer test (local)
- VAS scale
- PCR test for detection COVID-19
- Urine pregnancy test for women of childbearing potential
- ECG
- COVID-19–Impact on Quality of Life Questionnaire
- POST- COVID-19 Functional Status Scale

In case of **hospital discharge** within the study period, follow up will continue per protocol until day 28 wherever the subject will be located, depending on the status of the patient and study schedule.

	MGC Pharma Clinical Study Protocol	Protocol No.: MGC-009
		Version 02, 05 Sep 2021
		Page 46 of 76
A Phase IIb, double blind, placebo-controlled clinical study designed to evaluate the effect of CimetrA in patients diagnosed with COVID-19		CONFIDENTIAL

If patient discharged, visits will be performed via phone call, if he still hospitalized, visits will be performed at corona department.

Only on day 28, all the patients must undergo clinic visit , they will arrive to the research clinic.(only patient who will be under quarantine will have a phone call visit.)

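### The protocol contradicts itself on whether discharged patients give blood on day 7, and it fixes no day 4 draw for CRP and NLR, so the marker comparison may cover only patients still admitted.

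*Protocol*

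**What the plan says.** - **Endpoint.** Section 9.2 and the synopsis list change in IL-6, IL-1β, IL-12, TNF-α, IFN-γ, CRP and NLR. Section 9.2 ends the item with "NLR (Neutrophil / Lymphocyte ratio) (days 1, 2, 4, 7) compared to baseline".
- **Visit mode.** Section 10 states: "If patient discharged, visits will be performed via phone call, if he still hospitalized, visits will be performed at corona department". It adds: "Only on day 28, all the patients must undergo clinic visit", with a phone call instead for patients in quarantine. The end of section 10.2.1 repeats the rule: "If patient discharged, visits will be performed via phone call". The synopsis, under Study Duration, differs: follow-up after discharge is "performed via phone call or in-clinic, depending on the status of the patient and study schedule".
- **Day 7 bloods.** The day 7 list in section 10.2.1 has the cytokine sample and both routine panels, for example "Hematology blood test (local, mandatory even if there are available results from the day before". It does not restrict them to inpatients and describes no draw after discharge.
- **Days 3-6.** Table 5 shows a cytokine draw under days 3-6 without naming day 4. Haematology and biochemistry carry a double asterisk there, explained as "Measurements will be performed per institutional schedule by the hospital staff, not necessarily by the principal investigator or the sub-investigators". CRP belongs to the biochemistry panel, and NLR needs the blood count.
- **Analysis.** Section 17 compares the three groups on secondary outcomes by ANOVA or Kruskal-Wallis. Its multiple imputation is for binary data and the primary endpoint. Its last-observation rule covers patients with no post-baseline value, or withdrawn for an adverse event or intolerability.

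**The concern.** A phone visit yields no blood. Under sections 10 and 10.2.1, a patient who goes home before day 7 therefore has no day 7 marker value, although the endpoint and the day 7 list both call for one.

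These gaps would not be random. All patients are in hospital at entry, so discharge follows randomisation. On the WHO scale in section 9.1, an inpatient without oxygen scores 3 and an ambulatory patient scores 1 or 2, so going home is itself improvement on the primary scale. The patients without values would tend to be those who recovered sooner, and an effective treatment would change who they are. Randomisation does not protect a comparison restricted to patients still admitted.

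The protocol presents cytokine control as the product's rationale, and this is the outcome that tests it in patients. A statistical analysis plan could define how discharge is handled, but it cannot recover blood that was never drawn.

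The day 4 problem is separate. Even among inpatients, CRP and NLR exist on day 4 only where the ward happened to test.

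**Working it through.** **1. The passages side by side**

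| Item | Draw required? | Route after discharge |
|---|---|---|
| Section 9.2, days 4 and 7 | Yes, implied by the endpoint | None given |
| Section 10.2.1, day 7 list | Yes, panels mandatory | None given |
| Sections 10 and 10.2.1, visit mode | Not addressed | Phone until day 28 |
| Synopsis, Study Duration | Not addressed | Phone or clinic |

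These statements cannot all be followed for a patient discharged before day 7. Section 17 has no method for a marker missing because of discharge. Its remark that missing values are handled as ITT names no technique.

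**2. The plan's own figure**

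The sample size rests on the WHO scale, with no figure for markers. Inputs from section 17 are f = 0.20, α = 0.05 and 80 per group in 3 groups. With noncentrality f² × N = 0.04 × 240 = 9.6 and 2 and 237 degrees of freedom, power is 79.3%; 82 per group gives 80.4%. The stated power of at least 80% is reproduced within tolerance.

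**3. Illustration for day 7**

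These inputs are assumptions, not protocol figures:
- still admitted on day 7: p₀ = 0.50 on placebo, p₁ = 0.40 or 0.35 on active;
- correlation between marker change and length of stay: r = 0.3 or 0.5;
- bivariate normal model, with no true marker effect.

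*Bias.* The mean among those still admitted is r × λ(p) SD, where λ(p) = φ(z)/p and z cuts off the upper share p.
- λ(0.50) = 0.3989/0.50 = 0.798
- λ(0.40) = 0.3863/0.40 = 0.966
- λ(0.35) = 0.3704/0.35 = 1.058

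Bias = r × [λ(p₁) − λ(p₀)]:

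| p₁ | λ difference | r = 0.3 | r = 0.5 |
|---|---|---|---|
| 0.40 | 0.168 | 0.050 SD | 0.084 SD |
| 0.35 | 0.260 | 0.078 SD | 0.130 SD |

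The sign is against the active arm. If p₁ = p₀, the bias is zero.

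*Precision.* The numbers measured are 80 × 0.50 = 40 on placebo and 80 × 0.40 = 32 or 80 × 0.35 = 28 on active. The pairwise difference detectable with 80% power at two-sided 5% is 2.80 × √(1/n₁ + 1/n₂) SD.
- 80 vs 80: 2.80 × √(2/80) = 0.44 SD
- 40 vs 32: 2.80 × √(0.0563) = 0.66 SD
- 40 vs 28: 2.80 × √(0.0607) = 0.69 SD

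*Error rate.* The shift in the test statistic is bias divided by standard error. The smallest case is 0.050/0.237 = 0.21 and the largest is 0.130/0.246 = 0.53. The two-sided rejection rate with no marker effect moves from 5% to 5.5% and 8.3%. The chance of a false benefit falls from 2.5% to 1.5% and 0.6%.

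**4. Day 4**

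No figure is computed. The documents give no basis for the share discharged by then, and it may be small.

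**The case against.** The strongest reply is that the protocol does not settle that discharged patients go unsampled. The synopsis allows clinic follow-up, section 10 continues follow-up per protocol wherever the patient is, and the day 7 list has no inpatient restriction. This stands. A reader might infer that day 7 markers can be measured only in inpatients, but the documents support only a conflict in which one side has that result.

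A reader might also infer that many patients will be home by day 7, because entry requires room-air saturation of at least 94%. The documents do not show this. They give no discharge rate, the criteria also admit worsening disease, and exclusion on the ordinal scale begins only at score 5. Nor do they support treating day 4 as equally affected: the days 3-6 cytokine draw carries no institutional-schedule footnote, so only CRP and NLR have that weakness.

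Nor is the comparison necessarily biased between arms. Bias requires discharge to differ by arm. In the illustration it is well below the detectable difference, and it works against a claim of benefit. The main cost is lost precision.

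Finally, this is one of eight secondary outcomes, and trial success rests on the WHO scale, which Table 5 already schedules for the day 21 phone visit. That limits the weight of the point but does not remove the contradiction.

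**Conclusion.** The point holds as an internal contradiction with a conditional consequence. The endpoint and the day 7 list require blood, while sections 10 and 10.2.1 make visits after discharge phone calls until day 28. The synopsis alone leaves a clinic route open. If the phone rule is applied, the marker comparison, mainly at day 7, is confined to patients still admitted, and no stated missing-data rule covers this. The lack of a fixed day 4 draw for CRP and NLR holds whatever the discharge rate.

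The size is illustrative: 0.05-0.13 SD against active, and a detectable difference of 0.66-0.69 SD instead of 0.44 SD. It rests on the assumed shares still admitted and the assumed correlation. With equal discharge in the arms, there is a loss of precision and a result limited to inpatients, but no between-arm bias from discharge under this model. The trial's primary conclusion is not affected.

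**What to change.** 1. Reconcile the synopsis, sections 9.2 and 10, and the day 7 list and closing text of section 10.2.1 on whether discharged patients are sampled on day 7. If they are, name the route for the draw. The same decision should cover the day 14 bloods.
2. If they are not, state that the day 4 and day 7 marker results apply to patients still hospitalised. Report the number measured per arm and day, and make no between-arm efficacy claim from these results.
3. Schedule CBC and CRP on day 4 for inpatients, together with the cytokine draw already planned within days 3-6, and name day 4 for that draw.
4. Day 2 can be reported as the most complete post-baseline marker time point, noting that its draw is not timed against dosing. Making it the main comparison would be a debatable trade-off for that reason. Day 28 can serve as a late time point, noting that quarantined patients have only a phone visit.

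The cost is a wording amendment, a fixed day 4 panel in inpatients, and either a narrower day 7 claim or an added draw for discharged patients.

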10. STUDY DESIGN AND PROCEDURES

240 adult patients who suffer from COVID-19 infection and do not participate in any other clinical trial. Patient must not agree to participate in any new clinical study during the study duration. Study will take place during patient's hospitalization due to COVID-19 infection. The study will last up to 4 weeks, until conclusion on day 28. In case of hospital discharge within the study period, follow up will continue per protocol until day 28 wherever the subject will be located, depending on the status of the patient and study schedule.

If patient discharged, visits will be performed via phone call, if he still hospitalized, visits will be performed at corona department.

Only on day 28, all the patients must undergo clinic visit, they will arrive to the research clinic (only patient who will be under quarantine will have a phone call visit).

The study is not designed to include participants from a special population, so that patients with mental and intellectual problems, lack of judgment, children under the age of 18 and pregnant women will not be allowed to participate, or any patient who have a legal guardian.

Standard of care treatment acceptable to be used while patient participates in study:

Treatment will include:

Supportive care - symptomatic

Painkillers

Anticoagulant therapy

	MGC Pharma Clinical Study Protocol	Protocol No.: MGC-009
		Version 02, 05 Sep 2021
		Page 36 of 76
A Phase IIb, double blind, placebo-controlled clinical study designed to evaluate the effect of CimetrA in patients diagnosed with COVID-19		CONFIDENTIAL

Steroids

REMDESIVIR - Compassionate treatment

Antibiotic treatment as needed

Inhalations if necessary

Oxygen

The treatments offered above are given according to the guidelines of the Ministry of Health.

The treatment will be given to the patient according to the clinical judgment of the medical staff and in accordance with the patient's health condition, and therefore the treatment does not have to be the same in each of the medical centers participating in the study.

10.1. **Enrollment**

Each candidate subject will be reviewed for an inclusion/exclusion criteria. After signing the ICF, the candidate subject will be asked to provide a medical history and undergo a physical examination, including measurement of blood pressure, pulse, temperature (PO), body weight and height, saturation, respiratory rate, vas scale, news score.

Blood will be drawn for a complete blood count (CBC) and other laboratory analyses (Biochemistry, Pk-pharmacokinetics, Inflammatory markers, D-Dimer).

Women of childbearing potential must undergo a urine pregnancy test.

	MGC Pharma Clinical Study Protocol	Protocol No.: MGC-009
		Version 02, 05 Sep 2021
		Page 37 of 76
A Phase IIb, double blind, placebo-controlled clinical study designed to evaluate the effect of CimetrA in patients diagnosed with COVID-19		CONFIDENTIAL

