17. STATISTICAL METHODS AND DETERMINATION OF SAMPLE SIZE

A prospective, randomized (1:1:1), double-blind, multi-center, placebo-controlled clinical study.

Statistical Hypothesis

The hypothesis of this study is that treating with CimetrA and CimetrA2 will be more effective, while maintaining a favorable safety profile. This will be demonstrated by a significant difference between the two active and the control groups.

	MGC Pharma Clinical Study Protocol	Protocol No.: MGC-009
		Version 02, 05 Sep 2021
		Page 60 of 76
A Phase IIb, double blind, placebo-controlled clinical study designed to evaluate the effect of Cimetra in patients diagnosed with COVID-19		CONFIDENTIAL

In this study, we will test the following hypothesis:

- H0: $\Delta_1 = \Delta_2 = \Delta_3$
- H1: at least one is different.

Where Delta is the difference between baseline and end of study in WHO Ordinal Scale for clinical trial.

If the null hypothesis is rejected in favor of the alternative hypothesis the study will be deemed successful.

Safety will be assessed by adverse events, blood and urine laboratory assessments and vital signs.

Planned Sample Size

For this phase IIb, 3-armed clinical trial, we use the ANOVA test to estimate the expected improvement in the primary outcome; the WHO ordinal scale for clinical improvement.

We expect medium effect ($f=0.20$) for the differences in Delta between the 3 groups, and standard deviation of 1.5, based on the ordinal scale (0-8). This power analysis is for a one-way fixed effects analysis of variance with 3 levels. The study will include 80 patients per group for a total of 240 patients.

The criterion for significance (α) has been set at 0.05 with Power of at least 80%.

The analysis of variance is two-tailed Main effects.

For immunogenicity assessment, larger sample size will reduce mean variability in the observed outcomes and will increase the opportunity to detect real changes.

For 80 participants per group we ensure the desired precision for phase 3 trial to assess safety and effectiveness. Total sample 240 patients.

Computer Software

	MGC Pharma Clinical Study Protocol	Protocol No.: MGC-009
		Version 02, 05 Sep 2021
		Page 61 of 76
A Phase IIb, double blind, placebo-controlled clinical study designed to evaluate the effect of CimetrA in patients diagnosed with COVID-19		CONFIDENTIAL

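### The Day 28 visit, which supplies the primary WHO score, allows a phone contact only under quarantine, so other non-attenders can lose a score the protocol could still obtain

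*Protocol*

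**What the plan says.** Section 17 defines the quantity tested: "Where Delta is the difference between baseline and end of study in WHO Ordinal Scale for clinical trial". Section 10 fixes the end of study: "The study will last up to 4 weeks, until conclusion on day 28". The Day 28 score is therefore half of the primary outcome for every patient. The symptom score, the second primary efficacy outcome in section 9.1, is also due that day.

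On how Day 28 is conducted, section 10 says that all "patients must undergo clinic visit, they will arrive to the research clinic (only patient who will be under quarantine will have a phone call visit". Section 10.2.1 repeats this after the Day 28 procedure list, again with the exception "only patient who will be under quarantine will have a phone call visit". Table 5 labels the Day 28 column as a clinic visit.

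Other contacts are handled differently:

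- Section 10, for visits after discharge: "If patient discharged, visits will be performed via phone call".
- Section 10.2.1 heads one visit "Day 21 (phone visit". Its list includes the WHO score (run together with another item as "COVID-19–Impact on Quality of Life Questionnaire WHO Ordinal Score") and the symptom assessment; Table 5 agrees.
- Section 10.2.1 has study staff complete the WHO score from the patient's status, and the symptom score from status and answers. Neither is stated to need attendance in person.

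The synopsis (Study Duration) describes follow-up to Day 28 after discharge as "wherever the subject will be located, performed via phone call or in-clinic, depending on the status of the patient and study schedule".

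Section 11.3(e) withdraws participants who cannot or will not keep to the treatment, follow-up or safety schedule, and leaves them out of the primary analyses.

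**The concern.** The success test depends on one time point, and that is the one contact after discharge for which the phone is ruled out unless the patient is in quarantine. A discharged patient who is housebound, lives far away, or simply does not come has no stated route to a Day 28 score in sections 10 and 10.2.1. The synopsis suggests that a call might do, so a site cannot tell whether a Day 28 call to such a patient complies with the protocol.

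Two things are at stake. Missing scores cost power in a design with no stated allowance for them. Attendance may also depend on how the patient is doing, so the patients who are scored may not represent those randomised. Section 11.3(e) adds to this, because non-attendance can be read as failure to keep to follow-up and so as grounds for exclusion. This is a data-collection rule, and analysis cannot recover an observation that was never made.

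**Working it through.** **1. Is the Day 28 score obtainable by phone on the protocol's own terms?**

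| Contact | Route in the protocol | WHO and symptom scores due? |
|---|---|---|
| Days 7 and 14, discharged | phone | yes |
| Day 21 | phone | yes |
| Day 28, quarantined | phone | yes |
| Day 28, discharged, not quarantined | clinic only (sections 10, 10.2.1); phone or clinic (synopsis) | yes |

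Only the last row denies a phone route, and there the protocol's own sections differ.

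**2. The plan's power figure.** Inputs from section 17: one-way ANOVA with 3 groups, f = 0.20, SD 1.5, alpha 0.05, 80 per arm (N = 240), power at least 80%.

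Power = P(F′ > F crit), where F crit is the 95th percentile of central F with (2, N − 3) degrees of freedom, and F′ is noncentral F with the same degrees of freedom and noncentrality λ = N f².

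For N = 240, λ = 240 × 0.04 = 9.6 with df (2, 237), giving power 79.3%. The stated figure reproduces to within a point, marginally on the low side; 82 per arm (246 in total) gives 80.4%.

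**3. Power if Day 28 scores are missing.** The protocol gives no non-attendance rate, so the rates below are assumptions. Losses are taken as equal across arms and missing scores as not recovered. The last column is 80/(1 − rate), rounded up, times 3.

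| Missing | Scored per arm | N | λ | Power | Randomised to keep 80 scored per arm |
|---|---|---|---|---|---|
| 0% | 80 | 240 | 9.60 | 79.3% | 240 |
| 5% | 76 | 228 | 9.12 | 77.1% | 255 |
| 10% | 72 | 216 | 8.64 | 74.6% | 267 |
| 20% | 64 | 192 | 7.68 | 69.1% | 300 |

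Each 5% missing costs about 2 to 3 points of power.

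**4. Bias.** Suppose a fraction m of an arm is unscored, attenders have mean change A and non-attenders mean change M. The true mean is (1 − m)A + mM, so the mean among attenders is off by A − [(1 − m)A + mM] = m(A − M). The bias in a comparison of two arms is the difference between their values of m(A − M). The document gives none of these quantities by arm, so neither sign nor size can be derived.

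For scale, f = 0.20 with SD 1.5 means a standard deviation of group means of 0.30. If both active arms differ equally from placebo by d, that standard deviation is d√2/3, so d = 0.30 × 3/√2 = 0.64 points. Any bias has to be judged against that.

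**The case against.** The strongest reply is that an end-of-study clinic visit is a legitimate choice. PCR, blood tests, ECG and examination need attendance, and PCR bears on the primary endpoint itself: score 0 in section 9.1 refers to viral RNA, so a call may not separate 0 from 1. That stands, and it is why the clinic visit should remain the default. It does not justify leaving a non-attender unscored. The protocol accepts the same limit for quarantined patients and its other phone visits, and a call can still identify need for assistance, readmission or death.

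The synopsis is looser, so it is too strong to say that the protocol as a whole offers no other route. That stands as well, although the synopsis also defers to the study schedule, which makes Day 28 a clinic visit. The texts need reconciling.

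There is partial mitigation: a Day 21 phone score, planned imputation and a missing-data sensitivity analysis. However, section 17 describes multiple imputation for a binary outcome while the endpoint is a mean change, and limits last-observation-carried-forward to other cases.

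The power losses are measured against complete data, and a phone fallback would not recover everyone. That stands: the table bounds what a fallback could restore and does not estimate the effect of this rule alone.

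A reader might infer that patients still on a ward also lose their score. Section 10 rules this out, since visits for those still in hospital take place there. A reader might also infer that non-attendance removes poor outcomes from the worse arm. Nothing in the protocol supports a direction, because recovered patients skip visits too.

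**Conclusion.** The point holds as an inexpensive improvement to data collection. Sections 10 and 10.2.1 contain a rule that can lose an obtainable primary outcome for discharged, non-quarantined patients who do not attend on Day 28. The rule sits poorly with the synopsis, and section 11.3(e) may turn the loss into exclusion.

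Power falls from 79.3% to between 77.1% and 69.1% if 5% to 20% of Day 28 scores are missing. Those rates are assumed, equal across arms, with no recovery by imputation. Missingness related to outcome is a real risk, but its direction and size are unknown, and the documents support no bias figure. The flaw is not fatal to the trial; it is avoidable.

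**What to change.** In sections 10 and 10.2.1, keep the Day 28 clinic visit as the default for PCR, blood tests, ECG and examination. Replace the quarantine-only exception with wording such as: if a patient does not attend on Day 28 for any reason, the WHO score and vital status, and the symptom score where the patient can be contacted, will be obtained by phone call to the patient or caregiver, on the ward, or from hospital records, and the route will be recorded. Bring the synopsis into line, and state in section 11.3(e) that missing the clinic visit alone does not remove a patient from the primary analyses.

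The cost is a short wording change in a few places, one field for the route, and calls of a kind that sites already make on Day 21 and after discharge. No patients are added. The drawback is that phone-scored patients have no Day 28 PCR or blood results, so scores 0 and 1 may not be separable for them. Recording the route lets the analysis show how many patients this affects.
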